PROTOCOL COVER SHEET

Immediate Weight-bearing Verses Non-Weight-bearing after Foot & Ankle Surgery: A Prospective Analysis

04/29/2019

PRINCIPAL INVESTIGATOR [name], DPM, FACFAS

CO-INVESTIGATORS [name], DPM [name], DPM, FACFAS THE FOOT & ANKLE INSTITUTE STEEL VALLEY ORTHOPAEDIC AND SPORTS MEDICINE [name] [contact]

Email: [contact]

ABBREVIATIONS AND DEFINITIONS OF TERMS

NWB	Non-weight-bearing
WB	Weight-bearing
AE	Adverse event
SAE	Serious adverse event

ABSTRACT

In recent years, significant attention has been placed on the safety and efficacy of immediate weight-bearing following foot and ankle surgery. Returning patients to their previous activities as quickly as possible following surgery is always in the mind of providers, but the question of when has been difficult to answer.

Objectives:

The primary objective is to assess if immediate weight-bearing following foot and ankle surgery will yield equivalent, if not superior outcomes to the traditional non-weight-bearing post-operative course, while avoiding the undesirable effects commonly experienced during extended periods of non-weight-bearing. This will be determined by serial radiographs and/or other appropriate imaging modalities, physical exams and using patient self-reported pre- and post-operative SF-36 and AOFAS questionnaires.

Study Design:

Prospective, randomized controlled trial.

Setting/Participants:

Patients will be consented from 5 sites West Penn Hospital, Jefferson Regional Hospital, Forbes Regional Hospital, Bethel Park Surgery Center, and Monroeville Surgery Center and the level of care will include both inpatient and outpatient.

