2.1 Primary Objective (or Aim)

The primary objective of this study is to determine whether immediate weight-bearing following foot and ankle surgery provides similar or superior results to the traditional non-weight-bearing post-operative course, while reducing the disuse atrophy and length of rehabilitation necessary to recover during the transition to weight-bearing following an extended course of non-weight-bearing. This will be done by way of clinical follow-up, serial radiographs and/or other appropriate imaging modalities, and patient reported outcomes by way of AOFAS and SF-36 surveys.

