6.1 Primary Endpoint

The primary outcome measures are the American Orthopaedic Foot and Ankle Society (AOFAS) Ankle-Hindfoot Scale score and the SF-36 Health Survey Score as it pertains to the patient's ankle/foot. These assessments will be given to the patient in the pre-operative and post-operative periods.

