6.2 Secondary Endpoints

The secondary outcome measures are the frequency of complications during the perioperative and post-operative periods, osseous healing as assessed by both clinical and radiographic evaluation, and healing outcomes of soft tissue procedures. These results will be analyzed at the end of the follow-up period.

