6.5 Sample Size and Power

The study power calculation is based on the primary endpoints.

Assuming the American Orthopaedic Foot and Ankle Society (AOFAS) Ankle-Hindfoot Scale score and the SF-36 Health Survey Score (as it pertains to the patient's foot/ankle) are normally distributed in the immediate weight-bearing and non-weight-bearing groups and using an independent-samples t-test with a .05 two-sided significance level, and (absent any prior study results) assuming a "medium" effect size of Cohen's d = 0.40, 200 evaluable patients (100 patients in each group) would give you a power of 80% to detect a true difference in means on the questionnaires, if present. Fifteen patients will be added to each group for the potential of loss to follow-up. Final sample size is 230 patients (115 patients in each group). Sample size was calculated using an a-priori sample size calculator for Student t-tests (2017) available from http://www.danielsoper.com.

¹ "Effect size" is a statistical expression of the magnitude of the difference between two groups (Portney and Watkins, 2000). The standardized mean effect, one type of effect size, expresses the mean difference between two groups in standard deviation units. This is

typically reported as Cohen's "d." Interpretation of effect size depends on the research question. Cohen (1988) defines his effect sizes as: 8 = large (8/10 of a standard deviation unit). 5 = moderate (1/2 of a standard deviation). 2 = small (1/5 of a standard deviation). I would recommend using the "medium" effect size for your project. A medium effect size can range from 0.3 to 0.5.

SAFETY MANAGEMENT

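### The primary objective is to be judged on imaging, examination and questionnaires, but only the questionnaires are primary and powered, and the plan does not say which measures decide it

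*Combined protocol and SAP*

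**What the plan says.** Two parts of the document describe what the primary objective rests on.

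- **Abstract, Objectives:** "This will be determined by serial radiographs and/or other appropriate imaging modalities, physical exams and using patient self-reported pre- and post-operative SF-36 and AOFAS questionnaires".
- **Section 2.1:** the aim is to show that immediate weight-bearing "provides similar or superior results to the traditional non-weight-bearing post-operative course", and the means are given as "This will be done by way of clinical follow-up, serial radiographs and/or other appropriate imaging modalities", together with the AOFAS and SF-36 surveys. Section 2 gives the overall purpose as safety and efficacy.
- **Section 2.2:** the secondary objectives are procedure suitability, patient satisfaction, and return to work or sport. None names healing or complications.
- **Section 6.1:** "The primary outcome measures are the American Orthopaedic Foot and Ankle Society (AOFAS) Ankle-Hindfoot Scale score and the SF-36 Health Survey Score". Nothing else is listed as primary.
- **Section 6.2:** "The secondary outcome measures are the frequency of complications during the perioperative and post-operative periods, osseous healing", followed by soft-tissue healing.
- **Section 6.5:** "The study power calculation is based on the primary endpoints". The 80% is stated for a difference in questionnaire means.

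Healing and complications do have planned analyses. Section 6.4.1 gives imaging parameters one-way and two-way repeated-measures ANOVA, and compares complications and osseous healing between arms by chi-square. Section 7.3.1 has an outside statistician review data and adverse events after the first 10 patients in each arm. No margin, power or decision rule is attached to the 6.2 endpoints.

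**The concern.** In section 2, healing and clinical findings are part of the primary objective. In section 6 they are secondary endpoints, and no secondary objective in 2.2 corresponds to them. Satisfaction moves the other way: it is a secondary objective in 2.2 but the subject of the hypothesis that opens section 6. The two hierarchies do not map onto each other, and no text says which governs.

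This matters because 2.1 and the abstract claim similarity or equivalence. The protocol's own list of risks for the weight-bearing arm (6.8 and 7.3.2) consists mostly of healing and wound events: hardware failure, non-union, mal-union, delayed union, wound problems. AOFAS includes gait, motion and alignment items, but neither instrument measures union, repair integrity or complications. The similarity claim for those outcomes would therefore rest on a chi-square test for a difference, with no margin. If that test is non-significant, a report could take it as showing similar healing or safety, which it could not show at this sample size.

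**Working it through.** **1. The plan's own figure.** Inputs from 6.5: d = 0.40, two-sided alpha 0.05, power 80%, 100 evaluable per arm, plus 15 per arm for loss.

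- Normal approximation: n = 2(1.96 + 0.8416)² / 0.40² = 98.1, so 99 per arm. The noncentral t gives 99.08, so 100 per arm.
- Power at 100 per arm is 80.4% (t) or 80.7% (normal).
- 100 + 15 = 115 per arm, 230 in total.

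The figure reproduces. It covers the questionnaire means only.

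**2. Precision for a 6.2 rate at 100 per arm.** Half-width of the 95% interval for a difference, both arms at rate p: 1.96 × √(2p(1−p)/100).

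| p | Half-width (points) |
|---|---|
| 5% | 6.0 |
| 8% | 7.5 |
| 9.5% | 8.1 |
| 10% | 8.3 |

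Osseous healing applies only to patients with a bone procedure, and the documents do not give that number. If it were 50 per arm (an assumption), the half-width would be 8.5 points at 5% and 11.2 at 9%.

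**3. Power of the planned chi-square at 100 per arm.** Power = Φ[(d − 1.96·SE₀)/SE₁], where SE₀ = √(2p̄(1−p̄)/100) and SE₁ = √(p₁(1−p₁)/100 + p₂(1−p₂)/100).

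The contrasts are assumptions. The 5% rate is not in the documents. The rates 8%, 9.1% and 9.5% are in section 1.2 (two ankle-fracture series and one first metatarsophalangeal fusion series); they come from weight-bearing patients and are used only as plausible baselines. Doubling is also assumed.

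| Contrast | SE₀ | SE₁ | Power |
|---|---|---|---|
| 5% v 10% | 0.0372 | 0.0371 | 26.7% |
| 5% v 15% | 0.0424 | 0.0418 | 65.6% |
| 5% v 20% | 0.0468 | 0.0456 | 90.0% |
| 8% v 16% | 0.0460 | 0.0456 | 41.3% |
| 9.1% v 18.2% | 0.0486 | 0.0481 | 46.6% |
| 9.5% v 19% | 0.0494 | 0.0490 | 48.5% |

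**4. What this looks like in a result.** Suppose 8 of 100 and 16 of 100 patients have a complication. Chi-square = 200 × (8×84 − 16×92)² / (100 × 100 × 24 × 176) = 3.03, below 3.84, so p > 0.05. The difference is 8 points, with a 95% interval of 8 ± 1.96 × 4.56, or −0.9 to 16.9. The test is non-significant, yet the interval does not exclude an excess of nearly 17 points.

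**The case against.** The strongest reply is that healing and safety are already handled. They are named secondary endpoints, have planned between-arm tests, and are reviewed early under 7.3.1. Unpowered secondary safety endpoints are common. All of that stands, and 6.4.1, which holds the imaging and complication analyses, is itself headed as the analysis of the primary outcome. That heading blurs the hierarchy further, but it does not override 6.1 and 6.2.

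A reader might infer more than the documents support in three ways.

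- **That the primary objective can be declared met with healing and complications ignored.** The plan states no success rule at all, so this is an inference from silence. Section 2.1 still names clinical and imaging findings, and a report resting on questionnaires alone would contradict it.
- **That the plan claims 80% power for safety.** It does not; 6.5 ties the figure to questionnaire means.
- **That the sample size is wrong.** It is not; it reproduces.

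It is also fair to say that the power figures depend heavily on the contrast: at 100 per arm they run from 27% to 90% as the comparison rate rises from 10% to 20% against 5%. They illustrate what the secondary tests can bear; they do not measure the wording conflict itself.

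**Conclusion.** The inconsistency is plain in the text. The abstract and 2.1 put imaging and examination inside the primary objective; 6.1, 6.2 and 6.5 put them outside the primary endpoints and the power calculation; 2.2 gives them no objective. The documents leave open which measures decide the primary objective.

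The practical consequence is limited but real: a non-significant chi-square on healing or complications cannot carry the similarity claim. A doubling of the cited 8% to 9.5% rates would be missed more often than detected (power between 41% and 49%), and the expected interval is roughly 6 to 8 points either side at rates of 5% to 10%. These figures assume 100 evaluable patients per arm and the contrasts labelled above; bone-healing comparisons would have fewer patients and be less precise.

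The trial can run as designed. The correction should be made before results are known, because it determines what the main conclusion may claim.

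**What to change.** 1. **Abstract and 2.1.** State the primary objective as the comparison of AOFAS and SF-36 between arms, matching 6.1 and 6.5. Replace the similarity and equivalence wording with a difference between arms, since no margin is set.
2. **Section 2.2.** Add a named safety and healing objective tied to the 6.2 endpoints: complications, osseous healing and soft-tissue healing.
3. **Section 6.4.1.** Report each 6.2 endpoint as an arm difference with a 95% interval, next to the primary result. State that a non-significant chi-square will not be read as similar healing or safety.

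This costs wording only: no new data, visits or patients. The downside is a narrower primary claim and safety intervals that are openly wide.

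The alternative is to keep healing or complications within the primary objective as a co-primary endpoint, with a justified non-inferiority margin and its own power. That is a larger design choice. For scale, with equal true rates of 8% to 9.5%, one-sided alpha 0.025 and 80% power, n = 2p(1−p)(1.96 + 0.8416)²/margin². This gives 116 to 135 evaluable patients per arm for a 10-point margin and 463 to 540 for a 5-point margin. Both margins are assumptions, as the documents give none.

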2.2 Secondary Objectives (or Aim)

The secondary objectives are to:

- Determine if there are specific procedures better suited to immediate weight-bearing.
- Determine if patient satisfaction is higher in an immediate weight-bearing group compared to NWB.
- Determine if immediate weight-bearing allows earlier return to work and/or sport.

3 INVESTIGATIONAL PLAN

3.1 General Schema of Study Design

The study will be a randomized 1:1, controlled trial, prospective in nature, where participants undergoing foot and ankle surgery will be randomly placed into one of two

groups; an immediate weight-bearing group or a non-weight-bearing group. The patients will be randomly placed into the study group and control group if they meet all eligibility criteria. The first patient recruited will be assigned a unique study identifier (i.e., FAI001) and a coin flip will randomize the patient into either the study group (Heads) or control group (Tails). From that point, all patients will be placed into their groups by alternating between the control group and the study group. No bias will be placed on the subject or the procedure in regard to inclusion into a certain research group. Patients will be recruited and should they agree will be consented to the study with two year follow up results.

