The subjects will be identified/recruited during clinic hours as patients requiring an elective or traumatic foot and ankle surgery. During the clinic hours the primary investigator and/or the co-investigator will obtain full consent from the patient. We will recruit a minimum of 115 participants into each of two study arms, an immediate weight-bearing arm and a non-weight-bearing arm, so 230 participants will be included. Patients will be eligible if they are undergoing elective or traumatic foot and ankle surgery. Exclusion criteria will include any patient less than 18 years of age & over 89, history of foot or ankle surgery on the surgical limb, any degree of diagnosed peripheral neuropathy or peripheral vascular disease, infection, and/or unwillingness to participate at random in one of the two study arms.

Study Interventions and Measures:

We will be assessing the difference in two groups; immediate protected weight-bearing in a CAM walking boot vs strict non-weight-bearing for 6 weeks following foot and ankle surgery. Monitoring will be done by way of clinical follow-up, serial radiographs and/or other appropriate imaging modalities, and patient reported outcomes by way of AOFAS and SF-36 surveys.

Surgical procedures performed on patients included in the study will vary, as will the outcome measures for each procedure. Osseous fusions, including both elective joint fusions and bone healing following trauma, will be assessed by both clinical and radiographic evaluation. Soft tissue procedures, including elective stabilization and traumatic soft tissue repairs, will be assessed clinically and with imaging modalities

deemed appropriate. Complications during the perioperative and post-operative periods, such as non-union, infection, etc. will be included in the outcomes. All participants will also complete AOFAS and SF-36 surveys in the pre-operative and post-operative periods. We will also include return to work, activity, sport, etc. where appropriate.

Study Phase	Screening	Surgery	Post-op 2-3 w	Post-op 6-8 w	Post-op 3 m	Post-op 6 m	Post-op 1 yr	Post-op 2 yr	Unscheduled Visits
Visit Number	1		2	3	4	5	6	7	
Informed									
Informed Consent/Assent	x								
Review Inclusion/Exclusion									
Criteria	х								
Randomization	x								
Demographics/PMH	x								
Physical Examination	x		x	x	x	x	x	x	x
Adverse Event Assessment			x	x	x	x	x	x	x
Radiographs/Imagining	х		x	x	x	x	x	x	x
Complete AOFAS/SF- 36 survey	x			x	x		x	x	

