3.2 Study Duration, Enrollment and Number of Sites

This study will be conducted at 5 investigative clinic sites; West Penn Hospital, Forbes Regional Hospital, Jefferson Regional Hospital, Bethel Park Surgery Center, and Monroeville Surgery. Recruitment will stop when a minimum of 230 subjects are consented. The duration of the study for an individual patient will be two years from the surgery date. This will include the pre-operative assessment, surgery, regular post-operative appointments and a final two year follow-up, as noted in the table in the schedule of study section.

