3.2.2 Total Number of Study Sites/Total Number of Subjects Projected

The study will be conducted at 5 AHN investigative sites in the United States; West Penn Hospital, Jefferson Regional Hospital, Forbes Regional Hospital, Bethel Park Surgery Center, and Monroeville Surgery Center. Recruitment will stop when at least 115 subjects are randomly included in each of the two study arms. It is expected that approximately 230 subjects will be enrolled.

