3.3.2 Exclusion Criteria

- 1) Diagnosed peripheral neuropathy
- 2) Diagnosed peripheral vascular disease
- 3) Documented infection to the surgical extremity
- 4) Previous surgery to the surgical limb

- 5) Laboratory abnormalities that indicate clinically significant hematologic, hepatobiliary, or renal disease which would predispose patients to poor healing and/or non-union
- 6) Subjects who, in the opinion of the Investigator, may be non-compliant with study schedules or procedures.

Subjects that do not meet all of the enrollment criteria may not be enrolled. Any violations of these criteria must be reported in accordance with IRB Policies and Procedures.

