7.3.3 Potential Benefits of Study Participation

The potential benefits of study participation, namely for those participant randomly placed in the immediate weightbearing group of the study, would be those similar to benefits found in previous immediate or early weightbearing studies performed and mentioned in the literature review. These potential benefits would include:

- 1. The ability to bear weight on the surgical extremity in a protective boot.
- 2. Reduced muscle atrophy of the surgical extremity
- 3. Reduced stress on the non-surgical extremity
- 4. Reduced necessity of rehabilitation following healing of the surgical extremity
- 5. Increased quality of life during healing following foot and/or ankle surgery
- 6. Earlier return to work following foot and/or ankle surgery

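### The trial is called randomized 1:1, but after one coin flip every patient is assigned by alternation and no concealment is described

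*Combined protocol and SAP*

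**What the plan says.** The Abstract (Study Design) gives the design as "Prospective, randomized controlled trial", and section 3.1 says: "The study will be a randomized 1:1, controlled trial, prospective in nature". Section 3.1 then sets out the method. The first recruit gets an identifier (FAI001) and a coin flip, and after that: "From that point, all patients will be placed into their groups by alternating between the control group and the study group".

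The language of random assignment recurs in section 3.2.2 ("Recruitment will stop when at least 115 subjects are randomly included in each of the two study arms"), in section 7.3.3 ("namely for those participant randomly placed in the immediate weightbearing group of the study"), in the Abstract's exclusion of patients unwilling to accept either arm at random, and in the Randomization row of Table 1.

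These passages bear on who could act on knowledge of the next arm:

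- Abstract, Setting/Participants: "During the clinic hours the primary investigator and/or the co-investigator will obtain full consent from the patient".
- Sections 7.1.1 and 7.4 leave initial recruitment to the discretion of the participating surgeons.
- Section 3.3.2, criterion 6, excludes: "Subjects who, in the opinion of the Investigator, may be non-compliant with study schedules or procedures".
- Abstract, Study Interventions: the arms are a walking boot with immediate weight-bearing and six weeks of strict non-weight-bearing.

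Sections 3.1 and 6.3 both give assurances against bias. Neither names a mechanism.

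**The concern.** Alternation after one flip has two possible sequences, each the mirror image of the other. It balances numbers but does not protect prognosis, because the next assignment can be worked out from the last one. The arms look different, so the last assignment is easy to learn. A recruiter could then approach a patient, wait a day, or apply the non-compliance criterion according to which arm is next.

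The analysis would not repair this:

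- Section 6.4.1 adjusts scores for age, gender, BMI and diabetes only.
- Its logistic regression on patient and surgical characteristics looks for predictors of high scores. It does not adjust the comparison of arms.
- Analyses by procedure are exploratory, and center is expressly left out.
- The repeated-measures models include the screening visit, so a group-by-visit contrast can absorb a stable baseline difference. It cannot absorb a difference in expected recovery.

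Imbalance in procedure, injury severity, expected compliance or center would therefore stay in the estimates for both primary endpoints. A publication using the present label would also describe the comparison as randomized when it is not.

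**Working it through.** **The plan's own figure.** Section 6.5 uses d = 0.40, two-sided 5% and 80% power. The normal approximation gives 99 per group and the t-test 99.08, rounded up to 100. Power at 100 per group is 80.4% (t-test). Adding 15 per group gives 115, or 230 in total. The sample size reproduces and is not in dispute.

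**How much is random.**

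- One shared list: 229/230 = 99.6% of assignments follow from the flip. Someone who always knows the last assignment guesses (229 + 0.5)/230 = 99.8% correctly.
- Five site lists, each started by its own flip (an alternative reading): 225/230 = 97.8% are fixed, and (225 + 2.5)/230 = 98.9% are guessed correctly from local knowledge alone.

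**Shared list, recruiter knows only the last assignment at their own site.** Let p be the site's share of recruitment and assume accrual in random order. The number K of assignments elsewhere between two at this site has P(K = k) = p(1−p)^k. The next arm here is the opposite of the last when K is even:

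P(K even) = p / [1 − (1−p)²] = 1/(2−p)

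The site shares below are assumptions, since the documents give none. The last column is a simulation of one central list in varying blocks (2/4/6, 4/6 or 4/6/8), with the same limited knowledge and the same guess.

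| p | Alternation, 1/(2−p) | Varying blocks |
|---|---|---|
| 0.2 | 56% | 54% |
| 0.5 | 67% | 57–59% |
| 0.8 | 83% | 58–61% |

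**Recruiter knows every past assignment.** Alternation gives 99.8%. Varying blocks, guessing the under-filled arm, give 70.2% (2/4/6), 69.3% (4/6) and 68.0% (4/6/8). Simple randomization gives 50% whatever is known.

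**What a bias would do (illustration with assumed sizes).** Suppose there is no true effect and selective enrollment shifts the difference in means by δ standard deviations. At 100 per group the test statistic is centered on δ√(100/2) = 7.07δ. The two-sided 5% error becomes 10.9% at δ = 0.1, 29.3% at 0.2 and 56.4% at 0.3. The documents supply no value for δ.

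**The case against.** The strongest reply is that predictability depends on facts the protocol does not state.

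- **Shared list.** It is inferred from one first patient, one identifier and one flip. Section 7.2 speaks of random identification numbers, which weakens FAI001 as evidence of a common running order. This stands, so the 99.6% and 99.8% are conditional. Separate site lists would not help: the figures barely move, and local knowledge would then be enough.
- **Gain over blocks.** With five equal sites and own-site knowledge only, alternation is about 2 points more predictable than varying blocks (56% against 54%). This also stands. The gap is large where assignments are known across sites or one site dominates. The same investigators may well work at several sites, but the documents do not say.
- **Existing order of steps.** Section 3.1 already places patients only if they are eligible, and Table 1 lists consent and eligibility review ahead of randomization. The recommended release rule is therefore partly present. It does not stop someone from deducing the arm before deciding whom to approach.
- **Case mix.** The Abstract covers elective and trauma surgery on bone and soft tissue, and the data form lists 21 procedures. Section 6.3 and the SF-36 form refer to hindfoot fusion. On the narrower reading, imbalance in procedure matters less. Imbalance in severity, compliance and center does not.
- **Disclosure.** The method is stated openly and no actual bias is shown. Both are true. Neither makes the label correct or supplies concealment.

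**Conclusion.** The concern holds and must be fixed. On the protocol's own description the allocation is quasi-randomized, and nothing in the documents conceals the next arm. The label is wrong under either reading of the list: 97.8% to 99.6% of assignments are determined, depending on whether there are five lists or one. How far a recruiter could exploit this runs from 56% correct guesses (own-site knowledge, assumed share 0.2) to 99.8% (full knowledge of a shared list), against 50% under simple randomization. The size of any resulting bias is unknown. The severity rests on the incorrect label, the undescribed concealment, and the fact that neither later analysis nor more patients can restore what the allocation did not provide.

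**What to change.** Replace the coin-flip and alternation sentences in section 3.1 with text such as:

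> Patients will be assigned 1:1 from a computer-generated random sequence prepared by a person who takes no part in recruitment. The sequence will be concealed by central or database release, or by opaque, sequentially numbered envelopes. Each assignment will be released only after consent and eligibility have been recorded.

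Use permuted blocks of randomly varying size, with the sizes held in a restricted document, or use simple randomization. State whether there is one list or one per site.

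If alternation is kept, or for patients already assigned by it, write quasi-randomized wherever the allocation is now called random (Abstract, Table 1, sections 3.1, 3.2.2 and 7.3.3) and in all reports. Name selection bias as a limitation.

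As a secondary point, say which stopping rule applies. Section 3.2 has "Recruitment will stop when a minimum of 230 subjects are consented", while section 3.2.2 requires at least 115 in each arm. Under alternation the two nearly coincide; under random allocation they can differ.

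**Cost.** Wording, a list, and some statistician and coordinator time. Preparing the list is a new task, because the outside statistician's only documented role is the safety review in section 7.3.1. The target stays at 115 per arm, and no visits are added.

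| Scheme | Stopping rule | Patients beyond 230 |
|---|---|---|
| One list, varying blocks, largest size B | ≥115 per arm | at most B/2 − 1: 2 if B = 6, 3 if B = 8; mean 0.2–0.3 |
| Five site lists, equal accrual (assumed) | ≥115 per arm | mean 1.2–1.4, 95th percentile 4 |
| Simple randomization | ≥115 per arm | mean 12, 95th percentile 31 |
| Simple randomization | 230 in total | none |

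In the last case each arm lies between 100 and 130 with about 95% probability. At that extreme, 200 evaluable patients split about 87:113 (100 × 200/230 and 130 × 200/230), and power falls from 80.4% to 79.7%.
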